4.10 PK Analysis

The pharmacokinetic blood sampling will be listed with the date and time of sampling. This SAP describes only the analyses for the study objectives not involving the PK objectives. The PK objectives will be described in a separate analysis plan.

4.11 Modifications from the statistical section in the protocol

The protocol stated hypotheses with one-sided testing using less than and greater than symbols. This is corrected in the SAP to two-sided hypotheses, as planned, using equal and not equal symbols.

The protocol stated that Cochrane-Mantel-Haenszel test stratified by study site will be used for the primary analysis. However, this conflicts with the primary and key secondary hypotheses planned in the protocol which are not stratified, so this is revised in the SAP to match with the planned hypotheses.

Due to early termination of the study, the sample size will be much less than planned. As a result, the statistical power can be inadequate for the planned

gatekeeping methodology. Therefore, standard hypothesis testing methods may be used instead to analyze the data (see section 4.8).

5. Interim analyses

No interim analyses were planned.

6. Sample size and Power calculations

A total of 330 subjects were to be enrolled and randomized into 3 groups (1:1:1).

The EULAR response rate will be considered as primary parameter. See Appendix B for details on scoring and coding. There is a special interest in the percentage of subjects with an EULAR response category of good or moderate (good and moderate combined) and the percentage of subjects with an EULAR response category of only good. These subjects will be called EULAR responders and EULAR good-responders, respectively.

[figure not shown]

Primary endpoint:

- The percentage of EULAR responders (good + moderate) at Day 8

Key secondary endpoints:

- The percentage of EULAR good responders at Day 8
- The percentage of EULAR responders at Day 15
- The percentage of EULAR good responders at Day 15

[REDACTED]

[REDACTED]
[REDACTED]
[REDACTED]
[REDACTED]
[REDACTED]
[REDACTED]

The sample size calculation is based on estimates from [REDACTED]

[REDACTED]
[REDACTED]
[REDACTED]
[REDACTED]
[REDACTED]
[REDACTED]
[REDACTED]
[REDACTED]
[REDACTED].

Although the above described the planned sample size, the study enrollment did not reach the planned goal, and the study may likely have inadequate statistical power.

7. Tables, Listings and Figures

Below are the titles for the planned study tables, listings and figures

Table 1	Subject Distribution
Table 2.A	Subject Distribution By Center (ITT)
Table 2.B	Subject Distribution By Center (PP)
Table 3.A	Demographics and Baseline Characteristics (ITT)
Table 3.B	Demographics and Baseline Characteristics (PP)
Table 4	Medical and Surgical History (ITT)
Table 5.A	Dose Administration (ITT)
Table 5.B	Dose Administration (PP)
Table 6.A	Dose Administration by Visit (ITT)
Table 6.B	Dose Administration by Visit (PP)
Table 7.A	Dose Administration by Center (ITT)
Table 7.B	Dose Administration by Center (PP)
Table 8.A	EULAR Good/Moderate Responders - Original and Simplified Analyses (ITT)
Table 8.B	EULAR Good/Moderate Responders - Original and Simplified Analyses (PP)
Table 9.A	EULAR Response by Visit (ITT)
Table 9.B	EULAR Response by Visit (PP)
Table 10.A	Time to First EULAR Good/Moderate Response (ITT)
Table 10.B	Time to First EULAR Good/Moderate Response (PP)
Table 11.A	DAS28 Scores (ITT)
Table 11.B	DAS28 Scores (PP)
Table 12.A	Tender and Swollen Joints (ITT)
Table 12.B	Tender and Swollen Joints (PP)
Table 13.1.A	Visual Analog Scale (VAS) – Patient Pain (ITT)
Table 13.1.B	Visual Analog Scale (VAS) – Patient Pain (PP)
Table 13.2.A	Visual Analog Scale (VAS) – Patient RA Disease Activity (ITT)
Table 13.2.B	Visual Analog Scale (VAS) – Patient RA Disease Activity (PP)
Table 13.3.A	Visual Analog Scale (VAS) – Investigator RA Disease Activity (ITT)
Table 13.3.B	Visual Analog Scale (VAS) – Investigator RA Disease Activity (PP)
Table 14.A	American College of Rheumatology (ACR) 20/50/70 Response (ITT)
Table 14.B	American College of Rheumatology (ACR) 20/50/70 Response (PP)
Table 15.1.A	SF-36 Physical Component Score (ITT)
Table 15.1.B	SF-36 Physical Component Score (PP)
Table 15.2.A	SF-36 Mental Component Score (ITT)

Table 15.2.B	SF-36 Mental Component Score (PP)
Table 16.A	Health Assessment Questionnaire (HAQ) (ITT)
Table 16.B	Health Assessment Questionnaire (HAQ) (PP)
Table 17.A	Functional Assessment of Chronic Illness Therapy (FACIT) Fatigue Score (ITT)
Table 17.B	Functional Assessment of Chronic Illness Therapy (FACIT) Fatigue Score (PP)
Table 18	Maintenance Improvement at Week 12 (Day 85)
Table 19.A	Health Economics Questionnaire (HEQ) at Week (Day 85) (ITT)
Table 19.B	Health Economics Questionnaire (HEQ) at Week (Day 85) (PP)
Table 20.A	Laboratory Results (SAF)
Table 20.B	Laboratory Abnormalities (SAF)
Table 20.C	Laboratory Shift (SAF)
Table 21	Vital Signs (SAF)
Table 22	Physical Exam (SAF)
Table 23	12-Lead ECG (SAF)
Table 24.A	Concomitant Medications Summary (SAF)
Table 24.B	Concomitant Medications (SAF)
Table 25.A	Adverse Event Summary (SAF)
Table 25.B	Adverse Events
Listing 1	Subject Disposition
Listing 2	Subjects Excluded from the Analysis Populations (randomized subjects)
Listing 3	Protocol Violations (SAF)
Listing 4	Visit Windows (SAF)
Listing 5	Demographics and Baseline Characteristics (SAF)
Listing 6.A	Medical and Surgical History (SAF)
Listing 6.B	Medical and Surgical History with MedDRA Coding (SAF)
Listing 7.A	Dosing Administration (SAF)
Listing 7.B	Dosing Administration (cont'd) (SAF)
Listing 7.C	Doses Not Given According to Protocol – Interrupted (SAF)
Listing 7.D	Doses Not Given According to Protocol – Discontinued (SAF)
Listing 7.E	Doses Not Given According to Protocol – Adjusted Rate (SAF)
Listing 8	DAS28 Scores and EULAR Response (SAF)
Listing 9	Swollen and Tender Joints (SAF)
Listing 10.A	Visual Analog Scale (VAS) – Patient Assessment of General Health and Pain (SAF)
Listing 10.B	Visual Analog Scale (VAS) – Patient and Investigator Assessment of RA Disease Activity (SAF)

CLR_15_05 SAP

Listing 11	American College of Rheumatology (ACR) 20/50/70 Response (SAF)
Listing 12.A	SF-36 Physical and Mental Component Scores (SAF)
Listing 12.B	SF-36 Physical Functioning (SAF)
Listing 12.C	SF-36 Role Limitations Due to Physical Health (SAF)
Listing 12.D	SF-36 Role Limitations Due to Emotional Health (SAF)
Listing 12.E	SF-36 Social Functioning and Pain
Listing 12.F	SF-36 Energy/Fatigue
Listing 12.G	Emotional Well-Being
Listing 12.H	General Health
Listing 13.A	Health Assessment Questionnaire (HAQ) (SAF)
Listing 13.B	Health Assessment Questionnaire (HAQ) (cont'd) (SAF)
Listing 13.C	Health Assessment Questionnaire (HAQ) (cont'd) (SAF)
Listing 13.D	Health Assessment Questionnaire (HAQ) (cont'd) (SAF)
Listing 13.E	HAQ Scores (SAF)
Listing 14	Functional Assessment of Chronic Illness Therapy (FACIT) Fatigue Scale (SAF)
Listing 15.A	Health Economics Questionnaire (HEQ) – Use of Hospital Services (SAF)
Listing 15.B	HEQ – Use of Hospital Services (cont'd) (SAF)
Listing 15.C	HEQ – Use of Hospital Services (cont'd) (SAF)
Listing 15.D	HEQ – Use of Ambulatory Care Services (SAF)
Listing 15.E	HEQ – Use of Ambulatory Care Services (cont'd) (SAF)
Listing 15.F	HEQ – Other Expenses (SAF)
Listing 15.G	HEQ – Other Expenses (cont'd) (SAF)
Listing 16.A	Laboratory – Chemistry (SAF)
Listing 16.B	Laboratory – Hematology (SAF)
Listing 16.C	Laboratory – Urinalysis (SAF)
Listing 16.D	Laboratory – ESR (SAF)
Listing 17	Vital Signs (SAF)
Listing 18	Physical Exam (SAF)
Listing 19	12-Lead ECG (SAF)
Listing 20	Concomitant Medications (SAF)
Listing 21.A	Adverse Events (SAF)
Listing 21.B	Adverse Events (cont'd) (SAF)
Listing 22	PK Sampling (SAF)

Figure 1 Time to First EULAR Good/Moderate Response (ITT)

8. Statistical software

SAS version 9.3 or higher will be used for all tables, listings and figures.

9. References

Biometrical Journal. 50:708-714

[figure not shown]
10. APPENDIX A – Scoring and Coding for SF-36 – Short Form 36

Details for scoring SF-36 responses can be found at:

<https://www.rand.org/health/surveys-tools/mos/36-item-short-form/scoring.html>

Associated SAS code can be found below and at:

[figure not shown]
<http://gim.med.ucla.edu/FacultyPages/Hays/utils/sf36v2-4-public.sas>

11. APPENDIX B – Scoring and Coding for EULAR

	Change in DAS28 from baseline		
DAS28 after xx weeks	>1.2	>0.6 and \leq 1.2	\leq 0.6
\leq 3.2 (inactive)	Good	Moderate	No response
>3.2 and \leq 5.1 (moderate)	Moderate	Moderate	No response
>5.1 (very active)	Moderate	No response	No response

12. APPENDIX C – Scoring and Coding for DAS28

The DAS28 is a combined index for measuring disease activity in RA. The index includes the assessment of 28 joints for swelling and tenderness, acute phase response (ESR or CRP), and general health status. The index is calculated using the following formula:

$$\text{DAS28} = 0.56 \times \sqrt{\text{TJC28}} + 0.28 \times \sqrt{\text{SJC28}} + 0.70 \times \ln(\text{ESR}) + 0.014 \times \text{VAS}$$

where

[figure not shown]
TJC28 = tender joint count on 28 joints

SJC28 = swollen joint count on 28 joints

ln = natural log

ESR = erythrocyte sedimentation rate (mm/hr)

[figure not shown]
VAS = visual analogue scale, i.e., patient's global assessment of disease activity (100 mm VAS)

13. APPENDIX D – Scoring and Coding for ACR 20/50/70

The ACR core set of outcome measures and their definition of improvement includes a $\geq 20\%$ improvement (ACR20) compared to Baseline in both SJC and TJC as well as in three out of five additional parameters: Physician's Global Assessment of disease activity VAS, patient's Global Assessment of disease activity VAS, patient's assessment of pain VAS, HAQ-DI, and acute phase reactant (either CRP or erythrocyte sedimentation rate [ESR]).

Achievement of an ACR50 requires a $\geq 50\%$ improvement in the same parameters and an ACR70 requires a $\geq 70\%$ improvement.

14. APPENDIX E – Scoring and Coding for HAQ

The Stanford HAQ-DI is a patient-oriented outcome assessment questionnaire specific for RA. It consists of 20 questions referring to eight component sets: dressing/grooming, arising, eating, walking, hygiene, reach, grip, and activities. Each question asks on a scale ranging from 0 to 3 if the categories can be performed without any difficulty (scale 0) up to cannot be done at all (scale 3).

The patient must have a score for at least 6 of the 8 categories. If there are less than 6 categories completed, a HAQ-DI cannot be computed, whether the missing categories are due to missing values or they do not apply to the respondent.

In the event where there is a missing domain score but a corresponding aid or device is listed, then the score for that domain will reflect the use of the aid or device, i.e. it will be scored as 2.

If a domain consists of two questions and one response is missing, then the domain score will be the non-missing response but if both responses are missing, the domain score will be missing. If a domain consists of three questions and one response is missing, the domain score will be highest of the non-missing responses, but if two or more responses are missing, then the domain score will be missing.

The HAQ-DI will be set to missing if more than two of the domain scores are missing. In the event that one or two domain scores are missing the final HAQ-DI score will be derived by dividing the total of the remaining domain scores by the number of non-missing domains.

The HAQ-DI is usually analyzed by calculating scores. In each dimension ("dressing & grooming", "arising", "eating", "walking", "hygiene", "reach", "grip", "activities") the raw score is calculated as Max (Dimension Score) and corrected if aids and devices were used or help from another person was needed. When aids or devices or help are indicated by the patient, the score for the category item is raised from a 0 or a 1 to a 2, but if the patient's highest score for that sub-category is a 3, it stays a 3. The available categories scores are summed and divided by the number of categories answered which yields the Standard Disability Index.

15. APPENDIX F – Scoring and Coding for FACIT

The symptom-specific measure FACIT-F (Functional Assessment of Chronic Illness Therapy - Fatigue) was developed to assess chronic illness therapy with special emphasis on fatigue in the past 7 days and consists of 5 dimensions:

1. physical well-being (PWB: 7 items),
2. social/family well-being (SWB: 7 items),
3. emotional well-being (EWB: 6 items),
4. functional well-being (FWB: 7 items), and
5. additional concerns (FS: 13 items).

Each of the questions is categorically answered using the scales 0=not at all, 1=a little bit, 2=somewhat, 3=quite a bit, and 4=very much. The values of some items are reversed during score calculations, so that higher score values indicate more favorable conditions: negatively stated items are reversed by subtracting the response from '4'. Apart from the single dimension scores, 3 composite scores can be derived based on the 5 dimensions:

FACIT-F trial outcome index (TOI) with a potential range of 0 to 108,

FACT-G total score with a potential range of 0 to 108, and

FACIT-F total score with a potential range of 0 to 160.

The 13 items included in the dimension "additional concerns" will be used to calculate the brief score for FACIT-F (fatigue) scale (potential score range: 0-52).

When there are missing data, pro-rating subscale scores are acceptable as long as more than 50% of the items are answered in that subscale. Subscale scores can be prorated by multiplying the sum of the subscale by the number of items in the subscale, then dividing by the number of items actually answered:

Prorated subscale score=[Sum of items scores] x [N of items in subscale]/[N of items answered].

The total score is then calculated as the sum of the unweighted subscale scores. The FACT scale is considered to be an acceptable indicator of patient quality of life as long as overall item response rate is greater than 80% (i.e., at least 22 of 27 FACT-G items completed: first 4 domains).

To derive a FACIT-F Trial Outcome Index (TOI):

$$\frac{(\text{PWBscore})}{ } + \frac{(\text{FWBscore})}{ } + \frac{(\text{FSscore})}{ } = \text{FACIT-F TOI}$$

To Derive a FACT-G total score:

$$\frac{(\text{PWBscore})}{ } + \frac{(\text{SWBscore})}{ } + \frac{(\text{EWBscore})}{ } + \frac{(\text{FWBscore})}{ } = \text{FACT-G Total score}$$

To Derive a FACIT-F total score:

$$\frac{(\text{PWBscore})}{ } + \frac{(\text{SWBscore})}{ } + \frac{(\text{EWBscore})}{ } + \frac{(\text{FWBscore})}{ } + \frac{(\text{FSscore})}{ } = \text{FACIT-F Total score}$$

The Fatigue Subscale score is calculated as follows: the individual items scores are summed, multiplied by 13 and divided by number of items answered.

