2.1 Intent-to-Treat Population

All patients randomized into the study will be included in the ITT population, if at least one dose or a part of Nanocort IV/Placebo infusion or Depo-Medrol/placebo IM injection was administered and at least one post-baseline efficacy measurement was performed.

Patients will be analyzed within the original treatment group they were randomized to. All analyses will be completed for the ITT population. The main analyses for assessment of study success will be analysis of the primary endpoint on the ITT population (see section 4.8).

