2.2 Per-Protocol Population

The PP population is defined as a subset of the ITT population excluding major protocol violators. The following is a list of some of the conditions which, if met, would likely exclude the patient from the PP population:

- Violation of inclusion or exclusion criteria
- Breaking the blind
- Randomization irregularities
- Withdrawal from the study before week 12
- Current use of prohibited DMARDs or biological RA treatments per protocol
- Any other relevant violations observed during the conduct of the trial

Final specification of the criteria, definitions and processes are detailed in the 'Blinded Review Report of Deviations Leading to Exclusion from the Per-Protocol Analysis' document.

Patients will be analyzed based on the treatment received. Analyses on the PP population will be seen as supportive analyses. The primary and secondary efficacy endpoints will be analyzed for the PP population.

The list of protocol deviations leading to exclusion from the PP population will be finalized before database lock. During the blind data review before database lock the PP population will be defined by determining subjects not eligible for the PP population and the reason they cannot be included.

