4.1 General Statistical Considerations

Individual data listings will be provided for all subjects enrolled, sorted by treatment group, site, subject and time point. Summary tables will be presented for the safety population by treatment group.

Descriptive statistics for continuous variables will be number of subjects (N), mean (Mean), standard deviation (SD), median (Median), minimum (Min) and maximum (Max). For categorical variables, the absolute (N) and relative frequency

(%) will be tabulated. Confidence intervals (CI) for mean values will be added if appropriate.

The analyses of the primary and key secondary efficacy endpoint are described in sections 4.8.1 and 4.8.2.

Due to early termination of the study, the sample size will be much less than planned. As a result, the statistical power can be inadequate for the planned gatekeeping methodology. Therefore, standard hypothesis testing methods may be used instead to analyze the data.

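### Dose-administration summary tables (SAP Tables 5.A to 7.B) are planned on ITT and PP only, so a dosed subject without an efficacy measurement is in no exposure summary and the tables may not match the AE tables

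*Combined protocol and SAP*

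**What the plan says.** SAP section 7 gives titles only. Table 5.A begins "Dose Administration (ITT", Table 6.A "Dose Administration by Visit (ITT" and Table 7.A "Dose Administration by Center (ITT"; 5.B, 6.B and 7.B are the PP counterparts. In the same list, laboratory, vital signs, physical examination, ECG, concomitant medication and the AE summary (Tables 20.A to 25.A) are labelled SAF. So are Listings 7.A to 7.E, which cover dosing and, separately, interrupted, discontinued and rate-adjusted doses.

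The sets are defined as follows.

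- **ITT (SAP 2.1):** randomised, at least part of a dose given, "and at least one post-baseline efficacy measurement was performed". Grouping: "Patients will be analyzed within the original treatment group they were randomized to".
- **PP (SAP 2.2):** a subset of ITT, grouped by treatment received. Conditions likely to exclude a subject include "Withdrawal from the study before week 12".
- **SAF (SAP 2.4):** at least part of an infusion or injection plus a post-baseline safety assessment, grouped as treated.

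SAP 4.1 states: "Summary tables will be presented for the safety population by treatment group". The protocol's ITT definition (10.8) asks only for one dose after randomisation.

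**The concern.** Exposure is normally summarised on the set used for adverse events, so that the two can be read together. Here they are separated by a condition that has nothing to do with exposure, namely whether an efficacy measurement was obtained. A subject whose Day 1 infusion was stopped and who then left is the kind of subject that condition can remove.

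This matters for Nanocort because infusion reactions are its named product risk (protocol Summary and 6.4.1), AEs due to infusion reactions are a listed endpoint, and protocol 6.6 foresees slowing or halting an infusion. How often infusions were completed is thus part of the tolerability picture. SAP 4.9 has no exposure subsection, so the six titles are the only specification of how dosing will be summarised.

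**Working it through.** No figure in the plan needs reproducing. The check compares the set label of each dosing output with the set definitions.

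**Step 1: count the dosing outputs by set (SAP section 7).** Summary tables: 3 ITT, 3 PP, 0 SAF. Listings: 5 SAF, 0 ITT, 0 PP.

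**Step 2: follow two kinds of subject through the outputs.**

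| Subject | Tables 5.A, 6.A, 7.A (ITT) | Tables 5.B, 6.B, 7.B (PP) | AE summary 25.A (SAF) | Dosing listings 7.A to 7.E (SAF) |
|---|---|---|---|---|
| Dosed fully or in part, has a safety assessment, no efficacy measurement | Absent | Absent (PP lies within ITT) | Present | Present where applicable |
| Given another arm's treatment, has efficacy data | Under the randomised arm | Under the treated arm, if not excluded | Under the treated arm | Under the treated arm |

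The first row gives different denominators, the second different arms. In the second case the A and B versions of one table can also disagree with each other.

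**Step 3: find the source of the gap.** Under the protocol's ITT definition the first row would not arise. The efficacy condition enters in SAP 2.1. SAP section 4 undertakes to document differences from the protocol. SAP 4.11 lists three (two-sided hypotheses, the unstratified primary test, the consequences of early termination), and this condition is not among them.

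**Step 4: bound the effect per subject.** Suppose, although no table shells are given, that the tables report the proportion with an incomplete infusion. Let an arm have N subjects in SAF, x of them with an incomplete infusion, and let m of those x be missing from ITT. The difference between the SAF and ITT proportions is

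x/N − (x − m)/(N − m) = m(N − x) / [N(N − m)].

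Since x is at least m, this is at most m/N. With m = 1 and the planned N = 110, the bound is 1/110 = 0.9 percentage points. The SAP says the final sample is much smaller than planned but gives no number; at an assumed 40 per arm the bound is 1/40 = 2.5 points. The documents give no value for m.

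**The case against.** The case for leaving the tables alone has real substance.

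- **Little is hidden.** Listings 7.A to 7.E keep these subjects, and Listing 2 covers randomised subjects left out of the analysis populations. A reader might infer that early leavers disappear from the exposure results altogether. The documents do not support that: they are missing from the summaries only.
- **Infusion tolerability is already summarised on SAF.** SAP 4.9.6 plans rates of AEs related to the infusion, starting during it or within 24 hours of its end, and leading to drug withdrawal. This stands, and it limits what depends on Tables 5 to 7.
- **Few subjects should be affected.** Protocol 8.5 and 8.6 keep incompletely dosed subjects in follow-up, the early-termination visit includes DAS28, and diary VAS scores start on Day 2. This also stands, though the number need not be zero: subjects may leave at any time, and the return visit is requested only if possible.
- **SAP 4.1 is not a clean rule to breach.** Taken literally it would put efficacy tables on the safety set too, and SAP 2.1 says that all analyses are done for ITT. These are two loose general statements that need reconciling; the table list does not plainly violate one of them.
- **The PP tables are not complete by construction.** A reader might infer from the PP definition that Table 6.B must show near-complete second dosing. But SAP 2.2 lists conditions that would likely exclude a subject, incomplete dosing is not among them, and the final criteria sit in a separate document.

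None of this explains why dosing should be summarised on a set conditioned on efficacy data when its own listings and the AE summary are not.

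**Conclusion.** The point holds as a modest inconsistency in the choice of analysis set. All dosing summaries are on ITT or PP; a dosed subject without an efficacy measurement can be absent from every one of them; and their denominators and arms need not match the AE summary. No endpoint, hypothesis test or efficacy conclusion changes.

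The size cannot be derived from the documents and is probably small. The per-subject bound in the working assumes that the tables report completeness of infusion, which the titles alone do not establish.

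It is tempting to conclude that the omission flatters the Nanocort arms. That would require knowing how many such subjects there are and in which arms, and the documents give neither. The 9.7% in protocol 6.3 cannot stand in for this: it counts patients with infusion reactions in earlier studies, not stopped infusions or departures without efficacy data, and this trial uses a slower infusion.

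**What to change.** Produce Tables 5, 6 and 7 on the safety population, grouped as treated. For Day 1 and Day 15 separately, show the numbers of subjects with a completed, interrupted, discontinued or rate-adjusted infusion. ITT and PP versions may stay as supplementary tables.

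Reconcile the wording: limit the SAP 4.1 sentence on summary tables and the SAP 2.1 sentence on all analyses to the outputs they are meant to govern, and name exposure explicitly under SAF. If the efficacy condition in SAP 2.1 is kept, list it in SAP 4.11 as a difference from the protocol.

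The cost is a change of population and grouping in the table shells plus a few sentences of text. The data are already planned for Listings 7.A to 7.E, so nothing new has to be collected.
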